3. The definitions and epidemiology of MCI. MCI originally was defined by significant declines in delayed recall, otherwise intact general cognition, and no functional impairment. 44 Recent studies indicate an overall prevalence of MCI of 15 – 22% 71 with higher prevalence rates in older age groups or among those with depression 72. People with MCI show annual

conversion rates to dementia or AD ranging from 6% to 25% and from 50 – 100% over 5 years 73. Currently, MCI subtypes characterize memory or non-memory impairment, and whether single or multiple domains are impaired 74-76 MCI with memory impairment (a-MCI) is the most studied subtype. In a recent study of outcome in MCI subtypes, 76% of persons who progressed to AD had prior a-MCI 77. We will stratify groups by a-MCI status. By recruiting subjects with depression and memory complaints, it is feasible to increase the proportion of a-MCI subjects to 50% (46% in our pilot samples). MCI in LLD. Cognitive impairment is a hallmark of geriatric depression and may persist despite successful treatment of depression 42,78. Up to 50% of LLD subjects may have MCI diagnosis. 78,79 Lee (2007) reported that 54% of a remitter LLD sample met criteria for MCI 43. Two epidemiological studies found that 13-20% of subjects with depressive symptoms subsequently develop MCI over an average of 3-6 years 80,81. Lyketsos et al reported that 20% of subjects with MCI had concurrent depressive symptoms 82. Comorbid depression accelerates conversion from MCI to dementia 83. Among those with MCI, 63% had amnesic type and 37% had non-amnesic MCI 42. Depression and dementia share common risk factors: geriatric depression could be a prodrome of dementia 78 or lead to damage to the hippocampus through glucocorticoid cascade leading to dementia 84,78,85. The existing studies suggesting irreversibility of cognitive impairment used either SSRIs or TCAs. Drug combination that produce antidepressant and cognitive enhancement is likely to improve treatment response, but the evidence is lacking. Our treatment strategy of combining an SSRI with memantine may lead to improvement in memory, attention, and executive control, particularly in LLD subjects with MCI.

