Diagnosis of MCI. We will conduct consensus meetings to assign patients to diagnostic groups, according to MCI criteria that we have used in prior studies and clinical judgment. MCI criteria are: 1) The patient is neither cognitively normal nor demented; 2) a decline in cognition as reported by the subject or a collateral; 3) cognitive testing shows impairment and corroborates subjective report of decline; and 4) functional activities are not significantly impaired. Subjects will be classified as amnesic type MCI (a-MCI) if they show mild impairment in memory with or without other domains impaired. We will use performances between -1.5 and -2 (SD) below age and education norms on one of two screening memory tests; WMS-IV Logical Memory and WMS-IV Visual Reproduction 164 to denote mild impairment 45,75,165. We chose a -1.5 SD index, as this is most widely used 74 and will be most relevant for comparisons with other studies in the literature. We will stratify the groups by the presence of amnesic MCI (either single or multiple domains).
Age at onset of depression: we will explore the role of age at onset in heterogeneity of MCI and treatment response by stratifying groups by onset before or after age 60, as commonly defined.

Medical evaluation. All subjects will receive an initial medical assessment including a complete physical examination with neurological and neuropsychiatric examinations, electrocardiogram (ECG), and laboratory testing at baseline. These tests are used to rule out new-onset medical illnesses that could account for behavioral and cognitive symptoms. All abnormal physical or laboratory findings will be reported to subjects' primary physicians with the subject's consent. If abnormal physical or laboratory results are considered responsible for depression, the subject will be excluded from participation.

3) Baseline assessment.

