For example, application of TBM in preliminary data to the T1 images acquired from 8 subjects with major depression scanned at baseline and after receiving six ECT treatments showed significant treatment effects in the right anterior

temporal lobe, ACC white matter and the nucleus accumbens. These structural changes demonstrate treatment-associated plasticity and confirm detection of treatment change over a relatively short period of time, (2-3 weeks) ($r=.62$; $p<0.01$).

Fig.7. ECT-related brain changes, FDR-corrected p-values are overlaid on the group-derived MDT in color.

WM Hyperintensities (WMH). The 3D T2-space images will be used to visualize WMHs by employing a semi-automated WMH identifier. Briefly, WMH burden will be assessed based on the signal intensities of co-registered 3D MEMPR and T2-SPACE images, and population statistics on the spatial distribution and neighborhood structure of WM lesions. With every unit increase in WM burden, we will estimate % reduction in local brain tissue volume. GLM and multiple regression analyses will determine links between WM burden, clinical measures and vascular risk factors in each treatment group that may need to be controlled for.

Integration with Mood and Neurocognitive Measures. To test hypotheses about the relationships between imaging metrics and change in mood and cognition, we will derive domain summary scores for the 3 domains of interest, mood, memory, and executive function. Percent change in the mean Z scores will be calculated for each domain score and entered into analysis. We will first test the specific hypotheses described in the aims using separate GLMs for each MRI method. Integration of Predictive Variables. After analysis is complete on the predictive validity of each MRI measure, those that significantly predict remission/relapse or cognitive decline at follow-up will be combined for regression analysis. We will use the best single predictor in each modality. The final analysis will include a step-wise multiple regression analysis of clinical outcomes.

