Hypothesis 1. The primary outcome, namely responder/remitter status, will be compared between the esCIT+MEM and esCIT+PBO groups using chi-square statistics. Days to remission will be analyzed using the Kaplan-Meier survival method with treatment group as a stratification variable using the day on which response was observed as the event indicator. The survival function estimates the proportions achieving the response criterion, while the overall survival curve reflects speed of response. The independent variable is treatment group with two levels. A log-rank test will be used to assess the significance of any difference between treatment arms, and Cox regression to reflect the role of baseline covariates. We will also report the total time spent below the response threshold, compare summary statistics, and patterns of response within the patient over time. Analysis of change over time will be performed using linear mixed model analysis of covariance (SAS PROC MIXED). The linear mixed model permits flexible specification of the covariance structure of the repeated measures within patient, and allows analysis of incomplete cases using maximum likelihood. The outcome measures will be the HAM-D scores as well as cognitive domain scores (i.e. memory, processing speed, executive function) with the baseline rating/score on each domain as a covariate.

Hypothesis 2a. The role of brain neuroimaging biomarkers in variability of treatment response is examined in this Hypothesis. Predictor variables: We predict that baseline measures of neuroimaging biomarkers (white matter hyperintensity, regional gray or white matter volumes, hippocampal thickness and regional FDDNP binding levels) will be related to treatment outcomes. These predictions will be evaluated in the context of the models described above (i.e., general linear mixed model) by adding the posited prognostic variable as an additional predictor. Moderator variables: A limited number of exploratory analyses will be performed to evaluate possible moderators of each treatment strategy. Statistical evaluation of moderators will be done by including the posited moderator variable as an independent variable and evaluating the moderator x treatment group interaction term. Mediator Variables: We will evaluate the variable as a potential

mediator using a principal stratification framework.17,20

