Inclusion criteria: 1) The presence of a major depressive disorder diagnosed according to the DSM-IVr criteria; 2) A 24-item Hamilton Rating Scale for Depression (HAM-D) score of 20 or higher at baseline; and 3) Mini-Mental State Exam (MMSE) score > 24; 4) Age > 60 years old; 4) Include participants after discontinuing anti-depressants during a washout period. The washout period will be performed at least 14 days before starting the study and between the administration of escitalopram and MAOI and other antidepressants; except fluoxetine (there will be a 4 week washout period).

5.0 *Indicate the specific exclusion criteria for each of the groups of research participants in this study.

If there are any exclusion criteria based on gender, pregnancy/childbearing potential, race, ethnicity or language spoken, explain the nature of and scientific rationale for the exclusions.

Exclusion criteria: subjects will be excluded if they had any current and/or lifetime history of other Axis I psychiatric disorders (except unipolar MDD; and stable comorbid anxiety disorders and insomnia), or recent unstable medical or neurological disorders; diagnosis of dementia; those with known allergic reactions to escitalopram or memantine. We will also exclude participants from taking all anti-depressant psychotropic medication and MAOIs for at least two weeks prior to entering the study (four weeks for fluoxetine). Escitalopram has low potential for interacting with most other drugs, including beta blockers, neuroleptics, lithium, and alcohol. The serotonergic syndrome has been reported in combined use of reversible MAOI, meclobomide, and linezolid, an antibiotic, which is a reversible non-selective MAOI. The washout period will be performed at least 14 days should be allowed between the administration of escitalopram and MAOI and other antidepressants; except fluoxetine there will be a 4 week washout period. We will not discontinue effective antidepressants. The taper will be instructed by the primary care physician or the psychiatrist.

6.0 *How (chart review, additional tests/exams for study purposes, etc.), when and by whom will eligibility be determined?

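### The MRI integration models use percent change in domain Z scores, which has no stable size and, under the ordinary formula, the wrong sign whenever baseline is negative

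*Combined protocol and SAP*

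**What the plan says.** The rule is in view 10.1 (Study Summary), item 4.0, under Integration with Mood and Neurocognitive Measures. To relate imaging to change, "we will derive domain summary scores for the 3 domains of interest, mood, memory, and executive function". Then: "Percent change in the mean Z scores will be calculated for each domain score and entered into analysis". The models are stated next: "We will first test the specific hypotheses described in the aims using separate GLMs for each MRI method". Under Integration of Predictive Variables, the MRI measures are filtered, so that "those that significantly predict remission/relapse or cognitive decline at follow-up will be combined for regression analysis", ending in a step-wise regression. Cognitive decline is not defined there.

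No section gives the percent-change formula, the population that defines the Z scores, a shift to a positive scale, or a rule for baselines at or near zero.

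Item 6.0 (Hypothesis 1) treats overlapping outcomes differently. HAM-D and the cognitive domain scores go into a linear mixed model "with the baseline rating/score on each domain as a covariate".

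**The concern.** Percent change needs a scale with a true zero and values of one sign. A Z score has neither: its zero is the mean of whatever reference is chosen.

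Baselines in the troublesome range should be expected here. If Z is standardised to the trial sample, baselines straddle zero by construction, in every domain. If Z is taken against published norms, memory is still exposed. The a-MCI rule is "We will use performances between -1.5 and -2 (SD) below age and education norms on one of two screening memory tests", and the background section says that "it is feasible to increase the proportion of a-MCI subjects to 50" percent. Mood against non-depressed norms is the likely exception, because entry requires "A 24-item Hamilton Rating Scale for Depression (HAM-D) score of 20 or higher at baseline", which puts all patients well to one side of zero.

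These models are tied to the stated aims. Hypotheses 2a and 4 name improvement in cognitive performance among the outcomes that imaging markers should predict and moderate. A real association could be missed or reported with the wrong sign. If cognitive decline in the marker-selection sentence is also measured this way, a marker could be dropped or enter the step-wise model reversed.

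**Working it through.** The plan attaches no power or sample-size figure to this analysis, so there is none to reproduce.

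**Arithmetic.** Let B be baseline and F follow-up. The ordinary formula is 100 × (F − B)/B.

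| B | F | True change | Percent change | With the absolute value of B as denominator |
|---|---|---|---|---|
| −1.0 | −0.5 | +0.5 | −50% | +50% |
| +1.0 | +0.5 | −0.5 | −50% | −50% |
| −1.5 | −2.0 | −0.5 | +33.3% | −33.3% |
| +0.1 | +0.6 | +0.5 | +500% | +500% |
| −0.1 | +0.4 | +0.5 | −500% | +500% |
| 0 | any | any | undefined | undefined |

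The first two rows are an improver and a decliner with the same score. An absolute-value denominator corrects direction but not the explosion near zero.

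**Patient level.** Assumed: true change has mean +0.3 and SD 0.5, independent of baseline. With baseline mean 0 and SD 0.75 to 1, 50% of patients get the wrong sign, 7.5-9.9% exceed ±500%, and the correlation of percent change with true change is about 0.00. The wrong-sign share is 75% at mean −0.5 and 91% at mean −1 (SD 0.75), and 99.9% at mean −1.5 (SD 0.5).

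**Detecting a marker.** Inputs:
- From the document: n = 100, the 50 + 50 completers of the power analysis in item 6.0.
- Assumed: marker M ~ N(0,1); B ~ N(μ, SD) with SD 0.7 or 1; F = μ + 0.4 + 0.7(B − μ) + 0.3M + error; error SD = SD × √(1 − 0.49).
- Two-sided 0.05 test, 10,000 trials per setting, ordinary least squares.

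| Baseline mean | Ordinary percent change: association detected |
|---|---|
| 0 | 7%, sign right about half the time |
| −0.5 | 7-10% |
| −1 | 10-25% |
| −1.5 | 19-59% |

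Across the three negative means, 66-99% of the significant results have the wrong sign. On the same simulated data, follow-up Z adjusted for baseline detects the association in 98-100% and the simple difference F − B in 96-100%. Percent change on the absolute baseline detects it in 28-72%, with almost no reversal.

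**Memory against norms.** Assumed: half the sample uniform between −2 and −1.5, the rest normal with mean −0.5 to +0.5 and SD 0.8, error SD 0.7, n = 100. Then 63-87% of baselines are negative, 74-91% of improvers are reversed and 5-6% of patients exceed ±500%. Detection is 6.5-11%, against 98% baseline-adjusted.

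**Mood against non-depressed norms.** At an assumed mean of +3, at most 0.2% of patients whose score rises are reversed, and percent change detects the association in 65-98%.

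**Fewer scans.** With an assumed 60 patients with MRI data, percent change detects 7% at mean 0 and 7-57% at means −0.5 to −1.5, against 87-99% baseline-adjusted.

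**The case against.** The strongest reply is that item 6.0 already provides for checking normality, transformations and influential observations, which would catch the exploding values. That has some force. If values beyond 1.5 interquartile ranges are clipped (an assumed rule, since the plan names none) and the absolute baseline is the denominator, detection recovers to 85-100%, and to 89-92% in the memory case. But the plan never states that denominator. With the ordinary formula, clipping leaves detection at 6-8% at mean 0 and makes 97-100% of the significant results wrong-signed at negative means. An improver scored at −50% is not an outlier, and the log transform named as an example is undefined for negative values.

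Three further points:
- The a-MCI band applies to one of two screening tests, not to a domain composite, so placing half the sample between −2 and −1.5 is a simplification. This is fair, but a softer composite for that half (mean −1, SD 0.6) still gives only 7-11% detection.
- If every baseline lay far below zero (mean −1.75, SD 0.25), percent change would be nearly a mirror image of true change (correlation −0.98) and could be recovered. A sample mixing patients with and without a-MCI is unlikely to meet that condition.
- The assumed marker effect is favourable, with a partial correlation of about 0.39 to 0.51. Halving it lowers detection by the simple difference to about 46-78%. The size of the contrast depends on this input; the sign reversal does not.

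It is also true that item 6.0 and the imaging section ask different questions, so different metrics need not conflict. The point is that the plan already contains a sound method for the same cognitive domains.

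**Conclusion.** The concern holds. As written, the rule is invalid for a signed score with an arbitrary zero; this is more than missing detail. Sign reversal follows by arithmetic from the ordinary formula, and instability near zero affects either denominator. The damage is greatest when baselines straddle or approach zero, which is certain under sample standardisation and likely for memory against norms. The detection rates rest on assumed inputs and are illustrations, not forecasts.

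The reach is limited to the MRI integration models and, if cognitive decline is measured this way, the step-wise model they feed. The primary remission comparison, the survival analyses, the mixed models in item 6.0 (including the Hypothesis 2a imaging predictors) and marker selection on remission or relapse are untouched. It should be fixed before analysis.

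**What to change.** In Integration with Mood and Neurocognitive Measures:
- Replace percent change with follow-up domain Z as the outcome and baseline Z as a covariate, or use the simple Z difference.
- Standardise both visits to the same stated baseline mean and SD, and give the Z reference and scoring direction for each domain.

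In Integration of Predictive Variables, define cognitive decline at follow-up on that same scale. Reconcile both paragraphs with the models in item 6.0.

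The cost is one or two sentences in the analysis plan, with the same data and no extra visits.

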7) **Follow up assessment:** The follow up will take place weekly for the first 4 weeks of treatment and every 2 weeks for the remaining 5 months of the 6 months trial, followed by naturalistic follow up monthly up to 12 months. Each follow up assessment will include measures of efficacy and safety. The need for repeated assessments stems from our hypothesis of difference in time-to-remission occurring during the extension treatment. The weekly frequency of contact with all subjects will serve as an additional safeguard to monitor worsening of depression, as well as the emergence of side-effects or suicidal ideations. All assessment procedures described below are identical for the two groups. Most of the instruments have been administered in our ongoing studies, and our subjects age 60 and older tolerate their administration quite well (Table 2).

Primary outcomes will be measured and defined as follows: 1) Remission will be defined as HAM-D scores of 6 or less for 3 consecutive weeks, week 12 and at 6 months visit; 2) Depressive relapse is defined as an episode of major depressive disorder that occurs within 6 months after remission, while 3) recurrence is defined as another depressive episode that

occurs after 6 months have elapsed.

Assessment and monitoring of suicidal risk will occur at each visit and by phone between visits. We have applied the standard procedures that are required and approved by the UCLA Institutional Review Board. We have employed the same procedures in our ongoing studies of late-life depression since 1995, and have had no suicide attempts among our subjects. We will monitor suicidal ideations using the 3rd item of the Hamilton Depression Scale during each visit to the site and the Beck Scale of Suicidal Ideations (SSI). Monitoring for SI will be done at each visit independent of the outcome assessment.

Monitoring of expectations for symptomatic improvement: Since subjects will enter the treatment process for symptomatic improvement, we will account for a differences in expectations between the two groups. Thus, subjects' expectations for improvement will be assessed during the baseline visit, at week 12, at the end of the acute treatment trial (Week 24), and during follow up. We will control for any differences in the analyses.

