Power analysis. The power analysis is focused on the primary aim of the study to assess whether the group receiving combined MEM and escitalopram demonstrate remission (HAM-D<6) compared to the other group. In the PI's pilot data, we observed remission in 83.3% of patients receiving the combination esCIT+MEM, compared to 30.7% in those receiving esCIT+PBO. In line with the message of Kraemer, et al. (2006) emphasizing that it is not safe to ignore uncertainty in pilot-study estimates of effect size, which risks underpowering the subsequent study, we derive a sample size appropriate to an effect considerably smaller than the observed difference. Specifically, we work with an assumption that the remission rate in the esCIT+MEM arm would be 70% (smaller than the observed rate of 83.3%) and that the remission rate in the esCIT+PBO arm would be 40% (larger than the observed rate of 30.7%). More involved analyses would be possible that average over a range of scenarios; the approach used here captures the essential feature that it is important to allow for possible regression to group means that are less different than those observed in the pilot study. We will draw on frameworks from the Institute of Medicine report on avoiding missing data,²² but if we recruit a total of 134 patients (67 per group) with a projected 25% dropout rate, we will be able to compare 50 completers in the esCIT+MEM group with 50 subjects in the esCIT+PBO group. Assuming that 70% of the group receiving esCIT+MEM respond versus 40% of the control subjects, the power for this chi-square test, at the 0.05 level of significance with 1 degree of freedom, exceeds 80%. To assess the impact of the proposed sample size on other analyses, we also investigated a repeated-measures analysis of our pilot data with continuous HAM-D scores as an outcome, comparing the treatment groups at 24 weeks, using the baseline measure as a covariate. We found that the effects observed in the pilot data (but reassessing with the proposed sample size) yielded a power over 0.9. In addition, we will compare the groups on the number of days until response using survival analysis. If we combine the groups and assume 40% dropout, the power of the two-sided log rank test at the 0.05 level of significance will be 0.869 with the proposed sample size.

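### The primary remission endpoint is defined inconsistently, leaves two time points unranked, and cannot be applied literally on the visit schedule shown

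*Combined protocol and SAP*

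**What the plan says.** All places are in section 10.1 of the combined protocol and SAP.

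- **Item 4.0, part 7 (Follow up assessment).** The primary-outcomes paragraph reads: "Remission will be defined as HAM-D scores of 6 or less for 3 consecutive weeks, week 12 and at 6 months visit". Follow-up is "weekly for the first 4 weeks of treatment and every 2 weeks for the remaining 5 months of the 6 months trial". The same part adds: "The weekly frequency of contact with all subjects will serve as an additional safeguard". It does not say that HAM-D is rated at those contacts.
- **Item 6.0, Hypothesis 1.** "The primary outcome, namely responder/remitter status, will be compared between the esCIT+MEM and esCIT+PBO groups using chi-square statistics". No cut-off, duration or time point is given. The days-to-remission analysis in the same paragraph works by "using the day on which response was observed as the event indicator".
- **Item 6.0, Power analysis.** The primary aim is whether the combination group will "demonstrate remission (HAM-D<6) compared to the other group". The rates are introduced with "Assuming that 70% of the group receiving esCIT+MEM respond versus 40% of the control subjects". They are discounted from a 12-week pilot that used a score below 6. The only time point in the paragraph belongs to the continuous HAM-D analysis: "comparing the treatment groups at 24 weeks, using the baseline measure as a covariate".
- **Item 4.0, part 8.** Entry to continuation treatment also uses a score below 6.

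**The concern.** The cut-off, duration and time point decide who counts as a remitter. Here the definition, the test and the sample size do not share one set of the three. Two statisticians following the plan faithfully could report different primary results. The open elements could also be settled after the data are known.

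The duration has a second problem. It is written in weeks, while visits after week 4 are two weeks apart. Someone therefore has to reinterpret it before it can be programmed.

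Missing scores add to this. Section 14.1 item 3.0 and section 15.2 item 5.1 discontinue participants without response by week 8, before either named time point, and item 6.0 projects 25% dropout. The analysis is intent-to-treat, but the plan does not say how a participant without the required scores is counted.

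**Working it through.** **1. The three statements side by side (section 10.1)**

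| Place | Cut-off | Duration | Time point |
|---|---|---|---|
| Item 4.0, part 7, primary outcomes | 6 or below | three weeks in a row | week 12 and 6 months, relation not stated |
| Item 6.0, Hypothesis 1 | none | none | none |
| Item 6.0, Power analysis | below 6 | none | none for remission |

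**2. Can the duration be scored?** Part 7 gives visits at weeks 1, 2, 3, 4, then 6, 8, ..., 24. That is 4 weekly and (24 − 4)/2 = 10 two-weekly visits.

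- Sets of three scores one week apart: weeks 1–2–3 and 2–3–4 only. None ends at week 12 or 24.
- If the rule meant three consecutive scheduled visits, weeks 8/10/12 and 20/22/24 would serve. The plan does not say this.
- Item 5.0 numbers the two-weekly visits 7 to 14, which is 8. Totals: 2 + 4 + 8 + 6 = 20 under item 5.0, against 2 + 4 + 10 + 6 = 22 under part 7 (screening and baseline, weekly, two-weekly, monthly).

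**3. Reproducing the stated power.** Inputs from the Power analysis: 70% v 40%, alpha 0.05, 67 per arm, 25% dropout.

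- Completers: 67 × 0.75 = 50.25, so 50 per arm.
- Pooled rate: (0.70 + 0.40)/2 = 0.55. Null SE = √(2 × 0.55 × 0.45/50) = 0.0995. Alternative SE = √((0.21 + 0.24)/50) = 0.0949.
- Normal approximation: Φ((0.30 − 1.96 × 0.0995)/0.0949) = Φ(1.107) = 0.866.
- Exact: summing the binomial probabilities of all outcome pairs for which the uncorrected Pearson chi-square is significant gives 0.876.

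Both agree with the stated figure of over 80%.

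**4. Does that power carry over to the sustained rule?** The documents give no remission rate for a rule with duration. Two assumed cases (exact, 50 per arm) show why no direction follows:

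- 80% of remitters kept in each arm: 0.70 × 0.8 = 56% v 0.40 × 0.8 = 32%, power 0.700.
- 90% kept with memantine and 80% with placebo: 63% v 32%, power 0.896.

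**5. Type I error if the time point were chosen afterwards.** For two two-sided 0.05 tests with correlation ρ, the error is 1 − P(|Z₁| ≤ 1.96, |Z₂| ≤ 1.96) under a bivariate normal. With assumed ρ = 0.5, 0.7 and 0.9 it is 0.091, 0.084 and 0.070. If remission is required at both times, there is one outcome and one test at 0.05.

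**The case against.** The best defence is that only the primary-outcomes paragraph claims to define remission. The Hypothesis 1 text may simply defer to it, and the bracketed cut-off in the Power analysis is not offered as a redefinition. That is fair, and it narrows the problem. It does not remove it: the governing paragraph still leaves its two time points unranked and states a duration that the visits cannot supply, and the sample size is still not tied to that rule.

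There is also evidence for 6 months. Aim 1 (item 2.0) describes an acute comparison of that length, and part 7 treats week 24 as the close of the acute phase. This leans towards 6 months without settling it, since week 12 is named alongside it.

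The cut-off difference may be notation. The document handles inequality signs loosely elsewhere: the lay summary admits people aged 60, while section 11.1 item 4.0 prints an age above 60. It affects only a score of exactly 6, so it is minor.

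The assessment schedule, Table 2 and the fuller study plan listed under item 1.0 are not shown. They might add HAM-D ratings or clarify the rule.

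Two stronger readings are tempting and should not be drawn:

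- **That the rule cannot be evaluated at 6 months under item 5.0.** Eight two-weekly steps from week 4 reach week 20. But item 5.0 itself labels those visits as running to 6 months, so its visits 12 to 14 can end there. The 8 v 10 count is a bookkeeping mismatch.
- **That response is a further, competing definition.** Hypothesis 2b equates response with remitter status, and the Power analysis uses the two terms interchangeably. The Phenotypes paragraph lists them separately. This is loose wording.

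**Conclusion.** The concern holds. The primary endpoint is inconsistent across the places that define, test and size it, and its duration cannot be applied literally at either named time point on the schedule shown. The main gaps are the time point and the duration; the cut-off is secondary.

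A reader might infer that the trial is underpowered. The documents do not support that. The stated power is correct for its inputs (exact 0.876). Power for the sustained endpoint cannot be derived, and plausible assumptions move it either way.

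A reader might also infer that the type I error is already inflated. No text proposes picking the better time point. The range of about 0.07 to 0.09 applies only if the two are treated as alternatives and chosen after the data are seen, with correlations assumed between 0.9 and 0.5. Under a joint requirement there is no inflation. The weight of the point rests on the unfixed endpoint.

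**What to change.** Before unblinding:

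- State one primary remission rule identically in item 4.0 part 7, Hypothesis 1 and the Power analysis. It needs one HAM-D cut-off, a duration in consecutive scheduled visits (or none), and one primary time point or an explicit joint requirement. Label any other time point secondary.
- In Hypothesis 1, replace the combined responder/remitter term with remitter alone.
- State how a participant without the required scores is counted in the intent-to-treat chi-square test.
- Restate the assumed rates and power for the chosen endpoint.
- Reconcile the two-weekly visit counts in part 7 (10) and item 5.0 (8).
- The sponsor must also reconcile the cut-off for entry to continuation treatment in part 8 with part 7. No clinical rule is proposed here.

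The cost is wording and one power calculation. A rule without duration, or one using the visits at weeks 8, 10 and 12, needs no visits beyond those in either count. The downside is that the restated power may be less favourable.
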